#### 6.2.5 Immunologic Response Criteria

##### 6.2.5.1 Definition of Biologically Active Dose

- $\geq 50\%$  increase of the circulating absolute NK-cell number (product of absolute number of mononuclear cells and the proportion of NK cells) that is maintained for at least 1 week as determined by flow cytometry over the patient's pre-treatment NK-cell count (**APPENDIX B**). The baseline will be defined in each patient as the number of NK cells determined no more than 1 month prior to rhIL-15 administration.
- The study will aim at determining a range of biologically active doses meeting the above criteria.

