### 3.8.2 5 Day Schedule

Procedure	Pre-treatment		Days During-treatment 							After treatment			
	Screening	Baseline 	1	2	3	4	5	6	8	21±4 	End of Treatment 	Follow-Up Period 	End of Study 
CIV rhIL-15 treatment 			x	x	x	x	x	x 					
Pathology confirmed	x												
Performance status	x	x	x						x		x	x	x
History & physical exam 	x	x	x	x	x	x	x	x	x		x	x	x
Vital Signs  and Weight	x	x	x	x	x	x	x	x	x		x	x	x
NIH Advance Directives Form 													
Acute Care, Hepatic and Mineral Panels and LDH	x	x	x	x	x	x	x	x	x	x	x	x	x
Ammonia level	x		x						x				
I/Os			x	x	x	x	x	x	x				
CBC w/differential	x	x	x	x	x	x	x	x	x	x	x	x	x
Reticulocyte Count		x											
Hepatitis and HIV serology	x												
Thyroid function tests: TSH and T4	x									x	x		
Troponin T or I, based on availability of test in DLM		x	x										
Urinalysis	x												
EKG	x		x										
Pulmonary function tests	x												
HLA (A, B, C, DR, DQ) typing		x											
Tumor imaging and serum tumor markers 	x	x									x		
Serum βHCG 	x		x										
ANA, RF and anti-thyroid antibodies	x										x		
Pharmacokinetics (PK) 			x	x	x	x	x	x					
Serum immunoglobulin levels		x											
Flow cytometry ([name] Lab) 		x	x						x	x			
Flow cytometry ([name] Lab) 		x	x						x	x			
Cytokine and MesoScale inflammatory cytokines 			x	x	x	x	x	x	x	x			
Anti-IL-15 antibodies 			x							x		x	
Optional Tumor Biopsies 		x							x				

**Abbreviated Title:** Ph I Study of CIV rhIL-15

**Version Date:** 06/13/2018

1. All cycles are 21 days in length, but the end of cycle evaluations may be performed  $\pm$  4 days from this time point and an additional 7 days allowed for reasons other than recovery for treatment-related toxicities. Cycle 1 day 21 and cycle 2 day 1 maybe the same calendar day for certain patients. This also applies to later cycles where day 21 of a previous cycle falls on the same calendar day as day 1 of the subsequent cycle.
2. Patients whose best response after 4 consecutive cycles of treatment is stable disease will be followed with routine exams and restaging scans: Every 60 days x 3; then quarterly for up to 2 years after starting treatment unless progressive disease is documented, or they begin another treatment for their cancer.

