3. Denotes testing to be performed at an end of study visit (just prior to the patient being taken off study), if feasible.
4. Because the treatment is CIV for 120 hours, the day 5 treatment concludes on day 6.
5. Interval history during inpatient treatment period.
6. Vital signs, including heart rate, blood pressure, respiration, temperature and arterial oxygen saturation (SO2) by transcutaneous pulse oximeter.
  - a. Every 4 hours  $\pm$  1 hour during treatment days 1 through 6 (SO2 every 8 hours  $\pm$  1 hour)
  - b. Every 8 hours  $\pm$  1 hour on other inpatient days
  - c. Once at outpatient clinic follow-up visits on days 8 and 21.
  - d. Off treatment visit
  - e. End of study visit.
7. Repeat radiologic studies to assess response the last week (day 14 through 21) of even numbered cycles (2, 4, 6 and so on) as long as patients meet criteria to continue treatment. Patients with evidence of a partial or complete response (RECIST criteria) may undergo a confirmatory scan at least 4 weeks after the scan which first met the criteria for a clinical response. Patients with tumors known to have tumor markers (PSA, CEA, and CA125) will have the serum level of these markers assessed at the time of their radiographic restaging.
8. Pretreatment on Day 1 or within 3 days of starting treatment in women of child bearing potential.
9. PKs are collected on Cycle 1 only. Samples are collected in 4 mL SST tubes at the time points. These samples will be held at room temperature until picked up by the [name] laboratory (Blood Processing Core) for processing ([contact] for pickup). See Section [5.1](#) for additional details.
10. One 10 mL lavender-top tube will be drawn for Lymphocyte Phenotype IL-15 FACS analysis. If the Immunology Section Laboratory is unable to perform this analysis on the specified days, this assessment maybe omitted or replaced with standard TBNK panel. See Section [5.1.2](#) for additional details:
  - a. At baseline (need to perform twice before initiating study drug if at all possible.)
  - b. Day 1: prior to the start of the CIV rhIL-15 infusion
  - c. Days 8 and 21 drawn with the routine laboratories
11. Two 10 mL lavender-top tubes will be drawn for the [name] Lab (NIAID) to perform special FACS analysis. See Section [5.1.2](#) for additional details:
  - a. At baseline (need to perform twice before initiating study drug if at all possible.)
  - b. Day 1: prior to the start of the CIV rhIL-15 infusion

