  - c. Days 8 and 21 drawn with the routine laboratories
12. **Cytokine and MesoScale inflammatory cytokines are collected on cycle 1 only:** Samples to assess for IL-2R $\alpha$  IL-18, MIP2, MIP1 $\alpha$ , TNF $\alpha$  and MesoScale Discovery Multiplex Pro-inflammatory Cytokines (IL-1 $\beta$ , IL-12p70, Interferon  $\gamma$ , IL-6, IL-8 and IL-10) will be obtained from the same SST tubes drawn for PK time points drawn at the time listed in Section [5.1.3](#). Refer to this Section for additional details.
13. For all samples: Assessments that fall on a Friday, Saturday or Sunday due to an individual patient's treatment schedule will be shifted forward or backward to the nearest day that these laboratories are able to process the time sample.
14. Optional biopsies will be performed (if patient agrees) pre-treatment and one subsequent time between Day 8 and Day 21 as determined by clinical response and/or changes in lymphocyte subsets.
15. If baseline tests were already performed and meet the required time frames, they will not need to be repeated.
16. End of treatment visit will occur approximately 30 days after the last dose of study drug. If the patient cannot return to the Clinical Center, a request will be made to collect clinical labs from a local physician or laboratory. If this is not possible, patients may be assessed by telephone for symptoms.
17. All subjects will be offered the opportunity to complete an NIH advance directives form (Section [10.3](#)); preferably done at baseline, but can be done at any time during the study as long as the capacity to do so is retained. The completion of the form is strongly recommended, but is not required.

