#### 6.2.5.2 Secondary Biologic Study Endpoints

In mice and non-human primates, another sensitive indicator of biological activity following IL-15 administration has been the expansion of the T-memory phenotype CD44hiCD8+ (T-cell memory phenotype compartment in mice) cell. Therefore, the secondary biological endpoint will aim at determining signs of expansion of the counterpart T-cell population in humans.

- Doubling in the absolute number of CD45RO+ CD8+ T-cells that is maintained for at least 1 week as determined by flow cytometry over the patient's pre-treatment CD45RO+ CD8+ T-cell count. The baseline will be defined in each patient as the number of these cells determined no more than 1 month prior to rhIL-15 administration.
- The immunogenicity of the infused rhIL-15 will be defined using a 2-arm capture ELISA method (**APPENDIX B**).
- At least a 2-fold increase in serum soluble IL-2R-alpha (sIL-2R-alpha) levels.

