**APPENDIX E: CIV rhIL-15 BIOSPECIMEN WORKSHEET FOR 12-C-0113 CYCLE 2 AND BEYOND**

**Work sheet for 12-C-0113 Cycle 2**

Patient Name:		Start Date of Treatment: ___/___/20___			Dose Level: _____ mcg/kg/day				
		Start Time of Treatment: _____							
All samples should be kept at Room Temperature in Clean Utility Room Page until Pick up									
Page [name] Lab ([contact]) for Sample pick up				Page LyMB research nurse ([contact]) for sample pick up					
Study day	Sample name	Specimen Information			Ideal Sample Time	Actual Time Drawn	Pick up	Comments (Missed Specimens, etc.)	Signature
		Tube	Sample type						
1	IL-15 antibodies	1	4 ml SST	ELISA	Draw with AM Labs		[name]		
2	[name] FACS day 2	2	10 ml Lavender	Immune subsets	Draw with AM Labs		LyMB		
8	[name] FACS day 8	2	10 ml Lavender	Immune subsets	Draw with AM Labs				
12	[name] FACS day 12	2	10 ml Lavender	Immune subsets	Draw with AM Labs				
	IL-15 antibodies	1	4 ml SST	ELISA	Draw with AM Labs		[name]

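### Can the one-week biological activity criterion be scored on the 5-day schedule, where flow cytometry after dosing falls only on days 8 and 21?

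*Combined protocol and SAP*

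**What the plan says.** Section 6.2.5.1 sets the NK-cell criterion: a rise of at least 50% over the patient's own count before treatment, "maintained for at least 1 week as determined by flow cytometry". The baseline is a count taken no more than one month before rhIL-15. Section 6.2.5.2 asks for a doubling of CD45RO+ CD8+ T cells "that is maintained for at least 1 week as determined by flow cytometry". Section 6.2.5.1 adds that the study aims to find a range of doses that meet the criterion, and section 10.4 repeats that aim.

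Section 5.1.2 leaves the timing of flow draws to section 3.8. For the 5-day schedule, footnotes 10 and 11 of section 3.8.2 list baseline, day 1 before the infusion, and then "Days 8 and 21 drawn with the routine laboratories" for both panels. Footnote 1 says "All cycles are 21 days in length, but the end of cycle evaluations may be performed" up to 4 days either side of day 21. Footnote 13 says that samples due on a Friday, Saturday or Sunday "will be shifted forward or backward to the nearest day that these laboratories are able to process the time sample". Section 8 describes all secondary evaluations as exploratory.

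**The concern.** A duration criterion needs samples that can show duration. With one draw on day 8 and the next on day 21, a rise that lasted a week and ended before day 21 looks the same as one that vanished on day 9. The text does not say how many positive samples are needed, how a patient positive on day 8 only is classed, which of several eligible counts is the baseline, or how many patients make a dose active.

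The pattern is plausible. In the macaque study in section 1.2.1.3, lymphocytosis was still substantial a week after a 10-day infusion ended and near baseline two weeks after. Day 21 of the 5-day schedule falls 15 days after the infusion ends (21 − 6). Species, dose and cell measure differ, so this shows only that the case can arise.

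At stake is the reported range of active doses for the three 5-day levels: two analysts holding the same counts might class a patient differently.

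Appendix E, headed "CIV rhIL-15 BIOSPECIMEN WORKSHEET FOR 12-C-0113 CYCLE 2 AND BEYOND", adds to the doubt. It lists flow on days 2, 8 and 12 and names no schedule.

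**Working it through.** The documents give no sample size or power for this criterion, so there is no figure to reproduce. The check uses the draw days.

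**Gap between the two 5-day draws**
- Nominal: 21 − 8 = 13 days.
- With the 4-day window: 17 − 8 = 9 to 25 − 8 = 17 days.
- With the window and the Friday-to-Sunday shift: 7 to 19 days. This assumes the laboratories process Monday to Thursday. Example of the minimum: a Saturday start, day 8 moved to day 10, visit on day 17, so 17 − 10 = 7. Example of the maximum: day 8 moved to day 6, visit on day 25, so 25 − 6 = 19.

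**What each 5-day pattern shows** (patient negative before dosing on day 1)

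| Day 8 | Day 21 | What the samples show | Natural reading |
|---|---|---|---|
| + | + | Two positives 13 days apart, at least 7 in the extreme case | Met |
| + | − | Longer than 0 and under 21 − 1 = 20 days (under 16 if the last draw is day 17, under 24 if day 25) | Not met |
| − | + | One positive; duration open | Not met |
| − | − | No positive | Not met |

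All three ranges in the second row contain 7, so the true duration is undetermined. The classification is not: the criterion asks for a week of rise determined by flow, and one positive sample does not determine it. Two positives always satisfy it, even at the shortest gap, if the count is taken to stay up between them.

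**The same reading on the 10-day schedule.** Section 3.8.1 gives draws on days 8, 12, 21 and 28 in cycle 1, with gaps of 4, 9 and 7 days. Positive on days 8 and 12 and negative on day 21 shows at least 12 − 8 = 4 and under 20 days: not met, unless the special panel was already positive on day 2 (12 − 2 = 10 days). The reading carries over unchanged, although 10-day patients have more chances to show a week.

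**What depends on the result.** Escalation and the MTD rest on DLTs (sections 3.3 and 8). The 5-day expansion rests on a confirmed response (Schema). Neither uses the NK criterion. Patients covered on the 5-day schedule: at most 6 + 6 + 9 = 21. The documents do not allow an estimate of how many would be positive on day 8 only.

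**Baseline.** Section 6.2.5.1 defines the eligible window. Section 3.8.2 asks for two draws before drug if possible, plus a day-1 draw before infusion that may be one of the two. What is left open is a choice among two or three valid counts.

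**Appendix E.** Days 2, 8 and 12 are flow days of the 10-day special panel (section 3.8.1, footnote 12), and the 5-day calendar has no day-12 visit. The sheet therefore reads as a 10-day form with the schedule left off. Its day-12 row does conflict with footnote 2 of section 3.8.1, which limits day-12 tests to cycle 1. Section 3.8 governs through section 5.1.2.

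**The case for a change.** The strongest case for a change is that a rule would cost nothing. A sentence could define two positives at least 7 days apart as met, report single positives as duration not established, fix one baseline and give counts per dose. Finding a range of active doses is a stated aim, and section 10.2 ties a later paediatric protocol to a dose range with biological activity in adults. Reading an unconfirmed rise as not met will also label some real one-week rises as inactive.

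The last point stands: the natural reading is conservative, and more so on the 5-day schedule. A borderline patient could also change class with the choice of baseline. But the first part of the remedy only writes down what the wording already implies, and a separate class for single positives is a reporting preference that adds no information. Only a further draw at or after day 15 could separate the two cases (15 − 8 = 7), and the 5-day calendar has no visit between day 8 and the end-of-cycle window. The secondary objective in section 1.1.2 already calls for the changes in absolute counts, so the day-8 rise is reported whatever the duration class. A required number of patients per dose would have to be chosen without a basis in the documents; counts per dose serve an exploratory aim.

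**Conclusion.** The observation is correct: on the 5-day schedule a rise that lasts a week but ends before the day-21 draw cannot be confirmed, and the text does not spell out how such a patient is scored. It does not call for a change. The wording supports one workable reading that classes every pattern on both schedules, and the endpoint is exploratory, limited to at most 21 planned 5-day patients and outside every dosing decision. What remains is ordinary analyst work: show sample days with the counts, use one baseline throughout, and do not read a count of patients meeting the criterion as if both schedules could show duration equally well. The Appendix E mismatch is clerical.

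This rests on two assumptions. One is that a rise seen at both ends of an interval is taken as maintained between them. The other is that the opening of section 5 and the figure in Appendix B, which were not in the text I read, hold no different rule. If the criterion were later used to choose a dose, the scoring rule would need to be written first.

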#### 6.2.5.2 Secondary Biologic Study Endpoints

In mice and non-human primates, another sensitive indicator of biological activity following IL-15 administration has been the expansion of the T-memory phenotype CD44hiCD8+ (T-cell memory phenotype compartment in mice) cell. Therefore, the secondary biological endpoint will aim at determining signs of expansion of the counterpart T-cell population in humans.

- Doubling in the absolute number of CD45RO+ CD8+ T-cells that is maintained for at least 1 week as determined by flow cytometry over the patient's pre-treatment CD45RO+ CD8+ T-cell count. The baseline will be defined in each patient as the number of these cells determined no more than 1 month prior to rhIL-15 administration.
- The immunogenicity of the infused rhIL-15 will be defined using a 2-arm capture ELISA method (**APPENDIX B**).
- At least a 2-fold increase in serum soluble IL-2R-alpha (sIL-2R-alpha) levels.

### 6.3 TOXICITY CRITERIA

The following adverse event management guidelines are intended to ensure the safety of each patient while on the study. The descriptions and grading scales found in the revised NCI Common Terminology Criteria for Adverse Events (CTCAE) version 4.0 will be utilized for AE reporting. All appropriate treatment areas should have access to a copy of the CTCAE version 4.0. A copy of the CTCAE version 4.0 can be downloaded from the CTEP web site [http://ctep.cancer.gov/protocolDevelopment/electronic\\_applications/ctc.htm#ctc\\_40](http://ctep.cancer.gov/protocolDevelopment/electronic_applications/ctc.htm#ctc_40)).

## 7 SAFETY REPORTING REQUIREMENTS/DATA AND SAFETY MONITORING PLAN

### 7.1 DEFINITIONS

#### 7.1.1 Adverse Event

An adverse event is defined as any untoward medical occurrence in a human subject, including any abnormal sign (for example, abnormal physical exam or laboratory finding), symptom, or disease, temporally associated with the subject's participation in the research, whether or not considered related to the subject's participation in the research.

#### 7.1.2 Suspected adverse reaction

Suspected adverse reaction means any adverse event for which there is a reasonable possibility that the drug caused the adverse event. For the purposes of IND safety reporting, 'reasonable possibility' means there is evidence to suggest a causal relationship between the drug and the adverse event. A suspected adverse reaction implies a lesser degree of certainty about causality than adverse reaction, which means any adverse event caused by a drug.

#### 7.1.3 Unexpected adverse reaction

An adverse event or suspected adverse reaction is considered "unexpected" if it is not listed in the investigator brochure or is not listed at the specificity or severity that has been observed; or, if an investigator brochure is not required or available, is not consistent with the risk information described in the general investigational plan or elsewhere in the current application.

"Unexpected", also refers to adverse events or suspected adverse reactions that are mentioned in the investigator brochure as occurring with a class of drugs or as anticipated from the pharmacological properties of the drug, but are not specifically mentioned as occurring with the particular drug under investigation.

**7.1.4 Serious**

An Unanticipated Problem or Protocol Deviation is serious if it meets the definition of a Serious Adverse Event or if it compromises the safety, welfare or rights of subjects or others.

**7.1.5 Serious Adverse Event**

An adverse event or suspected adverse reaction is considered serious if in the view of the investigator or the sponsor, it results in any of the following:

- Death
- A life-threatening adverse drug experience
- Inpatient hospitalization or prolongation of existing hospitalization
- Persistent or significant incapacity or substantial disruption of the ability to conduct normal life functions
- A congenital anomaly/birth defect.
- Important medical events that may not result in death, be life-threatening, or require hospitalization may be considered a serious adverse drug experience when, based upon appropriate medical judgment, they may jeopardize the patient or subject and may require medical or surgical intervention to prevent one of the outcomes listed in this definition.

**7.1.6 Disability**

A substantial disruption of a person's ability to conduct normal life functions.

**7.1.7 Life-threatening adverse drug experience**

Any adverse event or suspected adverse reaction that places the patient or subject, in the view of the investigator or sponsor, at immediate risk of death from the reaction as it occurred, i.e., it does not include a reaction that had it occurred in a more severe form, might have caused death.

**7.1.8 Protocol Deviation (NIH Definition)**

Any change, divergence, or departure from the IRB-approved research protocol.

**7.1.9 Non-compliance (NIH Definition)**

The failure to comply with applicable NIH Human Research Protections Program (HRPP) policies, IRB requirements, or regulatory requirements for the protection of human research subjects.

**7.1.10 Unanticipated Problem**

Any incident, experience, or outcome that:

- Is unexpected in terms of nature, severity, or frequency in relation to
  - (a) the research risks that are described in the IRB-approved research protocol and informed consent document; Investigator's Brochure or other study documents, and
  - (b) the characteristics of the subject population being studied; **AND**
- Is related or possibly related to participation in the research; **AND**
- Suggests that the research places subjects or others at a *greater risk of harm* (including physical, psychological, economic, or social harm) than was previously known or recognized.

**7.2 NCI-IRB AND CLINICAL DIRECTOR (CD) REPORTING**

**7.2.1 NCI-IRB and NCI CD Expedited Reporting of Unanticipated Problems and Deaths**

The Protocol PI will report in the NIH Problem Form to the NCI-IRB and NCI Clinical Director:

- All deaths, except deaths due to progressive disease
- All Protocol Deviations
- All Unanticipated Problems
- All non-compliance

Reports must be received within 7 days of PI awareness via iRIS.

#### 7.2.2 NCI-IRB Requirements for PI Reporting at Continuing Review

The protocol PI will report to the NCI-IRB:

1. A summary of all protocol deviations in a tabular format to include the date the deviation occurred, a brief description of the deviation and any corrective action.
2. A summary of any instances of non-compliance
3. A tabular summary of the following adverse events:
  - All Grade 2 **unexpected** events that are possibly, probably or definitely related to the research;
  - All Grade 3 and 4 events that are possibly, probably or definitely related to the research;
  - All Grade 5 events regardless of attribution;
  - All Serious Events regardless of attribution.

**NOTE:** Grade 1 events are not required to be reported.

#### 7.2.3 NCI-IRB Reporting of IND Safety Reports

Only IND Safety Reports that meet the definition of an unanticipated problem will need to be reported to the NCI IRB.

### 7.3 IND SPONSOR REPORTING CRITERIA

During the first 30 days after the subject receives investigational agent/intervention, the investigator must **immediately** report to the sponsor, using the mandatory MedWatch form 3500a, any serious adverse event, whether or not considered drug related, including those listed in the protocol or investigator brochure and must include an assessment of whether there is a reasonable possibility that the drug caused the event. For serious adverse events that occur more than 30 days after the last administration of investigational agent/intervention, only report those that have an attribution of at least possibly related to the agent/intervention.

Required timing for reporting per the above guideline:

- Deaths (except death due to progressive disease) must be reported via email within 24 hours. A complete report must be submitted within one business day.
- Other serious adverse events including deaths due to progressive disease must be reported within one business day

Events will be submitted to the Center for Cancer Research (CCR) at: [[contact]](mailto:[contact]) and to the CCR PI and study coordinator.

